## 8 SAFETY ASSESSMENTS

Safety assessments will include injection site reactions, incidence and severity of nausea on a VAS (see list of endpoints in [Section 7.1.2](#)), clinical laboratory parameters, blood glucose monitoring, vital signs, ECGs, physical examinations, incidence and severity of treatment-emergent AEs, and C-SSRS.

### 8.1 Adverse Events

An AE is defined as any untoward medical occurrence in a clinical investigation subject administered a pharmaceutical product, which does not necessarily have a causal relationship with this treatment. An AE can therefore be any unfavorable and/or unintended sign (including a clinically significant abnormal laboratory finding), symptom, or disease temporally associated with the use of an investigational medicinal product, whether or not related to the investigational medicinal product. All AEs, including observed or volunteered problems, complaints, or symptoms, are to be recorded in the appropriate eCRF. The Investigator should update the appropriate eCRF if additional follow-up information becomes available (eg, the AE has subsided, stabilizes, or the condition becomes chronic in nature).

AEs, which include clinical laboratory test results, will be monitored and documented from the time of informed consent until study participation is complete. Subjects should be instructed to report any event that they experience to the Investigator, whether or not they think the event is due to study drug. From the time of informed consent, Investigators should make an assessment for AEs at each visit and record the event in the appropriate AE eCRF.

Wherever possible, a specific disease or syndrome rather than individual associated signs and symptoms should be identified by the Investigator and recorded in the eCRF. However, if an observed or reported sign or symptom is not considered a component of a specific disease or syndrome by the Investigator, it should be recorded as a separate AE in the eCRF. Additionally, the condition that led to a medical or surgical procedure (eg, surgery, endoscopy, tooth extraction, or transfusion) should be recorded as an AE, not the procedure itself.

Any medical condition already present at the time of informed consent should be recorded as medical history and not be reported as an AE unless the medical condition or signs or symptoms present at baseline change in severity, frequency, or seriousness at any time during the study. In this case, it should be reported as an AE.

Clinically significant abnormal laboratory or other examination (eg, ECG) findings that are detected during the study or are present at the time of informed consent and significantly worsen during the study should be reported as AEs. The Investigator will exercise his or her medical and scientific judgment in deciding whether an abnormal laboratory finding or other abnormal assessment is clinically significant. Thus, abnormal test results that are determined to be an error should not be reported as an AE, while laboratory abnormalities or other abnormal clinical findings (eg, ECG abnormalities) should usually be reported as an AE if any of the following are applicable:

- An intervention is required as a result of the abnormality;
- Action taken with the study drug is required as a result of the abnormality; or
- Based on the clinical judgment of the Investigator.

Clinically significant abnormal laboratory values occurring during the clinical study will be followed until repeat tests return to normal, stabilize, or are no longer clinically significant.

#### 8.1.1 Adverse Reaction

All noxious and unintended responses to a medicinal product related to any dose should be considered an adverse reaction. “Responses” to a medicinal product mean that a causal relationship between a medicinal product and an AE is at least a reasonable possibility, ie, the relationship cannot be ruled out.

#### 8.1.2 Unexpected Adverse Reaction

An unexpected adverse reaction is defined as an adverse reaction, the nature or severity of which is not consistent with the applicable product information.

#### 8.1.3 Assessment of AEs by the Investigator

The Investigator will assess the severity (intensity) of each AE and will also categorize each AE as to its potential relationship to study drug.

##### 8.1.3.1 Assessment of severity

Any local injection-site related AE (eg, pain, tenderness, erythema, and/or induration) should be documented and characterized as described in [Section 8.18](#). The severity of all other AEs should be graded according to the Common Terminology Criteria for Adverse Events (CTCAE) version 5.0. For those AE terms not listed in the CTCAE, the following grading system should be used:

- CTCAE Grade 1: Mild; asymptomatic or mild symptoms; clinical or diagnostic observations only; intervention not indicated;
- CTCAE Grade 2: Moderate; minimal local or noninvasive intervention indicated; limiting age-appropriate instrumental activities of daily living;
- CTCAE Grade 3: Severe or medically significant but not immediately life-threatening; hospitalization or prolongation of hospitalization indicated; disabling; limiting self-care activities of daily living;
- CTCAE Grade 4: Life-threatening consequences; urgent intervention indicated; or
- CTCAE Grade 5: Death related to the AE.

##### 8.1.3.2 Causality assessment

The relationship of an AE to the administration of study drug is to be assessed according to the following definitions:

- **No (not related or unlikely related):** The time course between the administration of study drug and the occurrence or worsening of the AE rules out a causal relationship and/or another cause (concomitant drugs, therapies, complications, etc) is suspected; or
- **Yes (possibly, probably, or definitely related):** The time course between the administration of study drug and the occurrence or worsening of the AE is consistent with a causal relationship and no other cause (concomitant drugs, therapies, complications, etc) can be identified.

Note: The definition implies a reasonable possibility of a causal relationship between the event and the study drug. This means that there are facts (evidence) or arguments to suggest a causal relationship.

The following factors should also be considered:

- **The temporal sequence from study drug administration:** The event should occur after the study drug is given. The length of time from study drug exposure to event should be evaluated in the clinical context of the event;
- **Underlying, concomitant, intercurrent diseases:** Each report should be evaluated in the context of the natural history and course of the disease being treated and any other disease the subject may have;
- **Concomitant drug:** The other drugs the subject is taking or the treatment the subject receives should be examined to determine whether any of them might be recognized to cause the event in question;
- **Known response pattern for this class of study drug:** Clinical and/or pre-clinical data may indicate whether a particular response is likely to be a class effect;
- **Exposure to physical and/or mental stresses:** The exposure to stress might induce adverse changes in the recipient and provide a logical and better explanation for the event; and
- **The pharmacology and PK of the study drug:** The known pharmacologic properties (absorption, distribution, metabolism, and excretion) of the study drug should be considered.

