### 3.6.1 Adverse Events (AEs)

AEs will be captured from the date of informed consent through study completion. All AEs will be coded to system organ class and preferred term using MedDRA version 27.0. Treatment-emergent adverse events (TEAEs) are defined as AEs that start after the first dose of study drug.

An overview of AEs will be provided including counts and percentages of subjects (and event counts) with the following:

- Any Adverse Events
- Any TEAEs (overall and by maximum severity)
- Any study drug related TEAEs (overall and by maximum severity)
- Any serious AEs (SAEs)
- Any treatment-emergent serious AEs (TESAEs)
- Any TEAEs leading to discontinuation of study drug
- Any TEAEs leading to discontinuation of study
- Any AEs leading to death

Counts and percentages of subjects (and event counts) will also be presented by system organ class and preferred term for each of the categories in the overview.

Listings will be presented specifically for SAEs, TEAEs leading to discontinuation of study drug, and TEAEs leading to discontinuation of study.

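### The causality categories in Protocol 8.1.3.2 are stricter than the protocol's own adverse-reaction standard and overlap each other, so drug-related TEAEs can be under-counted

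*Protocol*

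**What the plan says.** Protocol 8.1.3.2 offers two categories.

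- *No* (not or unlikely related) applies when the time course "rules out a causal relationship and/or another cause (concomitant drugs, therapies, complications, etc) is suspected".
- The other category opens "Yes (possibly, probably, or definitely related" and applies when the timing fits the drug and "no other cause (concomitant drugs, therapies, complications, etc) can be identified".

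A note under the two definitions adds: "The definition implies a reasonable possibility of a causal relationship between the event and the study drug". A list of further factors follows, to be weighed as well. It includes the class response pattern, concomitant drugs, stress and the drug's pharmacology. Nothing says that these factors override the two definitions.

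Protocol 8.1.1 defines an adverse reaction by a different test, namely that "a causal relationship between a medicinal product and an AE is at least a reasonable possibility, ie, the relationship cannot be ruled out".

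The SAP does not define relatedness. Its adverse event overview (SAP 3.6.1) has a line that begins "Any study drug related TEAEs (overall and by maximum severity", and the same category is broken down by system organ class and preferred term.

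**The concern.** The protocol holds two standards for the same judgement. Under 8.1.1, doubt about the cause leaves the event in. Under the 8.1.3.2 bullets, doubt takes it out: the joining words in *No* make a suspected alternative sufficient by itself, even when the timing fits perfectly. The usual reason for calling an event possibly related is that the drug is plausible and so is something else. The label of *Yes* includes that case, but its condition excludes it once the other cause is identified.

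Safety and tolerability is a secondary objective (Protocol 2.2), and the rationale for the product rests partly on tolerability (Protocol 1.4). The rating bears on:

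- the related-TEAE tables (SAP 3.6.1);
- reporting of SAEs after the follow-up call, which is limited to those the investigator considers related (Protocol 8.3.1);
- replacement, since subjects who discontinue for drug-related safety or tolerability reasons are not replaced (Protocol 4.3, which gives no relatedness test of its own). A discontinuation rated *No* becomes open to replacement at the sponsor's discretion;
- possibly, the classification of suspected unexpected serious reactions (Protocol 8.5).

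**Working it through.** The plan states no figure on this point, so the check is one of logic.

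**Definitions.** Let T mean that the timing fits the drug, S that another cause is suspected, and I that another cause is identified. An identified cause is also suspected, so I implies S. For this check, timing either fits or rules the drug out.

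- 8.1.3.2 *Yes* = T and not I.
- 8.1.3.2 *No* = not T, or S.
- 8.1.1 adverse reaction = the drug cannot be ruled out.

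| Case | Timing | Another cause | 8.1.3.2 bullets | 8.1.1 |
|---|---|---|---|---|
| a | rules drug out | any | *No* | not a reaction |
| b | fits | none suspected | *Yes* | reaction |
| c | fits | suspected, not identified | meets both *Yes* and *No* | reaction |
| d | fits | identified, does not exclude the drug | *No* | reaction |
| e | fits | identified, excludes the drug | *No* | not a reaction |

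The two sections agree in cases a, b and e. They conflict in case d. In case c the bullets give no unique answer, because *No* turns on suspicion and *Yes* on identification.

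**Direction.** Write n_b, n_c and n_d for the number of events in cases b, c and d.

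- Count under 8.1.1 = n_b + n_c + n_d.
- Count under 8.1.3.2 lies between n_b (every case c event rated *No*) and n_b + n_c (every case c event rated *Yes*).
- Shortfall lies between n_d and n_c + n_d.

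The shortfall is never negative. It is above zero once there is one case d event, or one case c event rated *No*.

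**Size.** Let q be the share of events meeting 8.1.1 that end up rated *No*. The related event count becomes (1 − q) times the 8.1.1 count. The documents give no value for q. As pure illustration, with 10 events meeting 8.1.1:

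- q = 10% leaves 10 × 0.90 = 9;
- q = 30% leaves 10 × 0.70 = 7;
- q = 50% leaves 10 × 0.50 = 5.

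These lines restate the assumption and estimate nothing. They also apply to events. SAP 3.6.1 reports subjects as well, and a subject stays in the related row if any one of her events is rated *Yes*, so the proportional fall in subjects need not equal q.

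**The case against.** The strongest reply is that the bullets should not be read alone. The note invokes a reasonable possibility, the *Yes* label admits possible relationships, and the factors send the investigator to the class pattern and the pharmacology. An investigator who weighs the whole section can arrive at the 8.1.1 standard. This stands in part: the section is ambiguous and does not force every doubtful event into *No*. It does not remove the conflict, because the stated conditions are stricter than the note and nothing ranks one above the other. Two careful investigators could rate the same event differently.

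A reader might infer three stronger things that the documents do not support.

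- *That the rule strips out the expected class effects, nausea and vomiting.* The class pattern is a listed factor, and Protocol 1.3 describes these events as dose-related and occurring at peak concentration. The design also limits competing causes: other medication is largely barred and GI motility disorders are excluded (Protocol 4.2), and meals are standardized in a confined unit (Protocol 3.1). The list of other causes in 8.1.3.2 is open-ended, so such events can be lost, but nothing shows that they usually would be. Nausea is in any case measured by VAS without a causality call (Protocol 8.14; SAP 3.6.8).
- *That serious reactions would go unreported.* All SAEs up to the follow-up call are reported whatever their cause (Protocol 8.3.1). Expedited reporting is the task of the sponsor or its designee (Protocol 8.5), and the adverse-reaction concept behind it is the inclusive one in 8.1.1. Only later SAEs depend expressly on the investigator's view. Section 8.5 does not say whose rating decides, so an effect there is possible but not shown.
- *That the active arms lose more events, biasing the comparison with placebo.* One rule applies to all arms under blinding (Protocol 5.3). The text does not determine how q differs by arm.

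**Conclusion.** The conflict holds. Sections 8.1.1 and 8.1.3.2 apply different relatedness standards, and the two categories in 8.1.3.2 overlap. Taken as written, the bullets give a related-TEAE count at or below the 8.1.1 count. That direction assumes that investigators follow the bullets and that an alternative cause does not exclude the drug merely by being suspected. The size cannot be derived from the documents, and neither can any effect on the contrast between arms.

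The reach is limited. All-cause TEAE tables, the nausea VAS summaries, reporting of SAEs up to the follow-up call and the food-intake model do not use the rating. What is weakened is the meaning of the related-TEAE tables and the consistency of the few decisions that rest on the same judgement.

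**What to change.** Replace the two definitions in Protocol 8.1.3.2 with one exhaustive, mutually exclusive pair aligned with 8.1.1:

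- *Yes*: a causal relationship with study drug is a reasonable possibility, that is, it cannot be excluded, even if another cause is also possible.
- *No*: there is no such reasonable possibility, for example because the timing excludes the drug or because another, established cause does.

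Make *No* the plain complement of *Yes*, with the timing and the established cause as examples only. If they were conditions, an event with no reasonable link to the drug and no established alternative would fit neither category. Keep the list of factors as aids to that single judgement. Put the same wording in the eCRF completion guidance, and state in SAP 3.6.1 that related means *Yes* under this definition. If events have already been rated under the current text, have them re-rated while the blind holds, so that one standard feeds the tables.

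The cost is two sentences, the guidance text and a minor amendment with the review and IRB approval that Protocol 12.1 requires. No assessment, sample size or model changes. The downside is a related-TEAE rate that may look slightly less favourable.

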## 8.2 Serious AEs

An AE or adverse reaction is considered serious if, in the view of either the Investigator or Sponsor, it results in any of the following outcomes:

- Death;
- A life-threatening AE;

Note: An AE or adverse reaction is considered “life-threatening” if, in view of either the Investigator or Sponsor, its occurrence places the subject at immediate risk of death. It does not include an event that, had it occurred in a more severe form, might have caused death.

- Requires hospitalization or prolongation of existing hospitalization;

Note: Any hospital admission with at least 1 overnight stay will be considered an inpatient hospitalization. An emergency room or urgent care visit without hospital admission will not be recorded as an SAE under this criterion, nor will hospitalization for a procedure scheduled or planned before signing of informed consent, or elective treatment of a pre-existing condition that did not worsen from baseline. However, unexpected complications and/or prolongation of hospitalization that occur during elective surgery should be recorded as AEs and assessed for seriousness. Admission to the hospital for social or situational reasons (ie, no place to stay, live too far away to come for hospital visits, respite care) will not be considered inpatient hospitalizations.

- A persistent or significant disability/incapacity or substantial disruption of the ability to conduct normal life functions;

- A congenital anomaly/birth defect; or
- An important medical event.

Note: Important medical events that do not meet any of the above criteria may be considered SAEs when, based upon appropriate medical judgment, they may jeopardize the subject and may require medical or surgical intervention to prevent one of the outcomes listed above. Examples of such medical events include allergic bronchospasm requiring intensive treatment in an emergency room or at home, blood dyscrasias or convulsions that do not result in inpatient hospitalizations, or the development of drug dependency.

### **8.3 SAE Reporting – Procedures for Investigators**

#### **8.3.1 Initial Reports**

All SAEs occurring from the time of informed consent until the follow-up phone call must be reported to Medpace Safety and Pharmacovigilance within 24 hours of the knowledge of the occurrence. After the follow-up phone call, any SAE that the Investigator considers related to study drug must be reported to Medpace Safety and Pharmacovigilance or the Sponsor/designee. Of note, reporting of SAEs after participation is complete is dependent on spontaneous reporting by the subject. The Investigator is not required to have further contact to elicit this information after completion of the final visit but should instruct the subject to contact the site to report any such events.

To report the SAE, complete the AE form with the SAE information electronically in the electronic data capture (EDC) system for the study. When the form is completed, Medpace Safety and Pharmacovigilance personnel will be notified electronically by the EDC system and will retrieve the form. If the event meets serious criteria and it is not possible to access the EDC system, send an email to Medpace Safety and Pharmacovigilance at [[contact]](mailto:[contact]) or call the Medpace SAE reporting line, and fax/email the completed paper SAE form to Medpace (contact information listed in [Section 8.6](#)) within 24 hours of awareness. When the EDC system becomes available, the SAE information must be entered as soon as possible.

#### **8.3.2 Follow-Up Reports**

The Investigator must continue to follow the subject until the SAE has subsided or until the condition becomes chronic in nature, stabilizes (in the case of persistent impairment), or the subject dies.

Within 24 hours of receipt of follow-up information, the Investigator must update the SAE form electronically in the EDC system for the study and submit any supporting documentation (eg, subject discharge summary or autopsy reports) to Medpace Safety and Pharmacovigilance via fax or email. If it is not possible to access the EDC system, refer to the procedures outlined above for initial reporting of SAEs.

### **8.4 Pregnancy Reporting**

If a subject becomes pregnant during the study, the Investigator is to stop dosing with study drug(s) immediately and the subject should be withdrawn from the study.

A pregnancy is not considered to be an AE or SAE; however, any pregnancy occurring during the study and up to 60 days after the last dose of study drug must be reported to Medpace Safety and Pharmacovigilance within 24 hours of knowledge of the event. Medpace Safety and Pharmacovigilance will then provide the Investigator/site the Exposure In Utero (EIU) form for completion. The Investigator/site must complete the EIU form and fax/email it back to Medpace Safety and Pharmacovigilance. Of note, reporting of pregnancy after the follow-up phone call is dependent on spontaneous reporting by the participant. The Investigator is not required to have further contact to elicit this information after completion of the follow-up phone call but should instruct the participant to contact the site to report any pregnancy which may occur after the follow-up phone call.

The pregnancy should be followed until the outcome of the pregnancy, whenever possible. Once the outcome of the pregnancy is known, the EIU form should be completed and faxed/emailed to Medpace Safety and Pharmacovigilance. If the outcome of the pregnancy meets the criteria for immediate classification as an SAE (ie, postpartum complication, spontaneous abortion, stillbirth, neonatal death, or congenital anomaly), the Investigator should follow the procedures for reporting an SAE.

## 8.5 Expedited Reporting

The Sponsor/designee will report all relevant information about Suspected Unexpected Serious Adverse Reactions (SUSARs) that are fatal or life-threatening as soon as possible to the Food and Drug Administration (FDA) and Institutional Review Boards (IRBs), and in any case no later than 7 days after knowledge by the Sponsor/designee of such a case. Relevant follow-up information will subsequently be communicated within an additional 8 days.

All other SUSARs will be reported, as applicable, to the FDA, other regulatory authorities, as applicable, and to the applicable IRB(s) as soon as possible but within a maximum of 15 days of first knowledge by the Sponsor/designee.

The Sponsor/designee will also submit any additional expedited safety reports required in accordance with the timelines outlined in country-specific legislation.

The Sponsor/designee will also inform all Investigators as required per local regulation.

The requirements above refer to the requirements relating to the study drug.

